	
3) The participant has already undergone an AVF or AVG procedure and is awaiting maturation.4) The participant has an active infection at the time of study enrollment.5) The participant has a presence of bacteremia or infection within 7 days prior to enrollment.6) The participant has a history neutropenia or a history of severe immunodeficiency disease.7) The participant has uncontrolled abnormal coagulation parameters and are at additional risk for clotting or excessive bleeding at time of enrollment per physicians opinion.8) The participant has a known allergy, intolerance or sensitivity to heparin, or previous incidence of heparin-induced thrombocytopenia.9) The participant has a known allergy or hypersensitivity to any of the device materials or Ethylene oxide (EtO).10) The participant has another medical condition or treatment, which in the opinion of the investigator, the participant may be non-compliant with the protocol, confound the data interpretation, or is associated with a life expectancy insufficient to allow for completion of study procedures and follow-up.11) The participant is currently participating in an investigational drug or another device study that has not completed the study treatment or that clinically interferes with the study endpoints. Note: Studies requiring extended follow-up visits for products that were investigational but have since become commercially available, are not considered investigational studies.
Study Methodology:	All participants will undergo a clinical evaluation at the Screening Visit (prior to Index Procedure). Participants that meet Eligibility Criteria will be consented, have the Pristine™ Long-Term Hemodialysis Catheter placed,

and will undergo additional follow-ups. Follow-up for all enrolled participants will be performed via in-person or telephone visit to the participant and dialysis center at 1-month, 3-months, 6-months, and 12-months post-Index Procedure.

	Screening	Index Procedure	Participant Follow-up				Unscheduled
			1-month (± 7 -days)	3-months (± 15 -days)	6-months (± 15 -days)	12-months (± 30 -days)	
In-Clinic Visit or Telephone Visit (Screening must be in-clinic visit)	X	X	X	X	X	X	
Informed Consent	X						
Eligibility	X						
Demographics	X						
Physical Examination	X						
Medical History	X						
Dialysis History	X						
Procedure Overview		X					
Study Device Details		X					
Hemodialysis Catheter Assessment			X	X	X	X	
Dialysis Session Logs			X	X	X	X	

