6 STUDY TREATMENT

All participants will undergo a clinical evaluation at the Screening Visit (prior to Index Procedure). Participants that meet Eligibility Criteria will have the BD Pristine™ Long-Term Hemodialysis Catheter placed and will undergo additional follow-ups. Follow-up for all enrolled participants will be performed via in-person or telephone screen to the participant and dialysis center at 1-month, 3-months, 6-months, and 12-months post-Index Procedure.

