8.1.1 Lost to Follow-Up

A participant will be considered Lost to Follow-Up (LTFU) if he/she repeatedly fails to return for/complete scheduled visits and is unable to be contacted by the investigational site. This does not apply to missed visits, where the participant misses one (1) follow-up visit but completes a subsequent one.

The following actions must be taken if a participant fails to return for/complete a required study visit:

- The site must attempt to contact the participant and reschedule the missed visit as soon as possible and counsel the participant on the importance of maintaining the assigned visit schedule and ascertain whether or not the participant wishes to and/or should continue in the study.
- Before a participant is deemed LTFU, the investigator or designee must make every effort to regain contact with the participant (where possible, 3 telephone calls and, if necessary, a certified letter to the participant's last known mailing address or local equivalent methods). These contact attempts should be documented in the participant's medical record and source documents.
- Should the participant continue to be unreachable, he/she will be considered LTFU effective the date of the final failed contact attempt.

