Legally Authorized Representative (LAR)	Individual or judicial or other body authorized under applicable law to consent, on behalf of a prospective participant, to the participant’s participation in the clinical investigation. “Legally designated representative” or “legally acceptable representative” are other terminologies used under national regulations for “legally designated representative”.
Line Reversals	Reversal of lumens of the catheter to allow for completion of HD treatment.
Lost to Follow-Up (LTF)	A participant may be considered LTF if the investigation site team members are unable to locate the participant despite three documented attempts to notify the participant via telephone and, if necessary, a certified letter to the participant’s last known mailing address or local equivalent methods. This does not apply to missed visits, where the participant misses one of the follow up contact time points but completed a subsequent one (when participant misses two consecutive follow-ups and is unable to be contacted with the documented attempts outlined before, the participant may be considered LTF and withdrawn from the clinical investigation). The site should also contact the HD center to ascertain the participant’s status. Before the site considers a participant LTF, written agreement should be obtained from the Sponsor.
Malfunction	Defined as a failure of a medical device to perform in accordance with its intended purpose when used in accordance with the IFU or CIP.
Mild AE	Awareness of a sign or symptom that does not interfere with the participant’s activity or is transient and is resolved without treatment or additional sequelae.
Moderate AE	Interferes with the participant’s usual activity and / or requires additional intervention and / or treatment and may have additional sequelae.
Monitoring	Act of overseeing the progress of a clinical investigation and to ensure that it is conducted, recorded, and reported in accordance

Term	Definition
	with this CIP, written procedures, applicable standards, and the applicable regulatory requirements.
Not Related AE	An AE is not related if it is determined that there is no plausible association.
Operator	Primary individual responsible for conducting the index procedure.
Point of Enrollment	Time at which, following recruitment and before any clinical investigation-related procedures are undertaken, a participant signs and dates the ICF.

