#### Non-infectious complications

Complication due to any noninfectious cause (thrombosis of the access, fibrin material within or around a catheter, catheter migration, central vein stenosis or thrombosis) requiring a revision procedure to maintain patency or improve access performance (i.e., thrombolysis, angioplasty, or surgical correction) in an inpatient or outpatient setting or removal or abandonment with creation of a new access that was not due to an access-related infection.

Subject will be considered as having a non-infectious complication and will be counted as an event if the subject has experienced a device-related non-infectious AE resulting in a re-intervention prior to the subject's end day of investigation period:

- **AE CRF Page:** Start Date of AE  $\leq$  End Day of Investigation period **AND** Relationship to study Device: Equals 'Related' or 'Likely Related' **AND** Was event infectious: Equals No **AND** Did AE Result in a Catheter Re-Intervention: Equals Yes; subject will be considered as a failure at AE start date

For each subject, the number of complications through the investigational duration is estimated as:

$$((\text{Number of observed infectious complications} + \text{Number of observed non-infectious complications}) * 1000) / \text{Length of investigation duration (Days)}$$

Length of investigation duration (Days) is from the date of index procedure to the end day of each subject's investigation period (End day of investigation period – Date of index procedure + 1); the end day of investigational period will be the earliest occurrence date of the following three events:

- If a subject's Pristine™ Catheter is removed due to Kidney Transplant, Transferred to AVG/AVF, Peritoneal Dialysis, Withdrawal of Care, or Other reasons, then the date of removal will be used to calculate the length of investigation duration. That is:
  - **Hemodialysis Catheter Re-Interventions CRF page:** Catheter removal Equals Yes **AND** Reason for catheter removal Equals: Kidney Transplant, Transferred to AVG/AVF, Peritoneal Dialysis, Withdrawal of Care, or Other; date of re-intervention is used in the estimation of investigation duration

$$\text{Length of investigation duration (Days)} = \text{Removal date} - \text{date of index procedure} + 1$$

- If a subject discontinues early, then the discontinuation date will be used to calculate the length of investigation duration.
 

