$$\text{Length of investigation duration (Days)} = \text{Discontinuation Date} - \text{Date of index procedure} + 1$$
- If the subject has not experienced any of the above events prior to the 3-months visit date, then the 3 months visit date will be used to calculate the length of investigation duration; in case of subject having the 3 months visit out of window and after day 105 or the subject misses the 3 months visit, then day 105 will be the end date of investigational period.
 
$$\text{Length of investigation duration (Days)} = \min((3 \text{ months visit date} - \text{date of index procedure} + 1), 105 \text{ days})$$

The analysis will be performed on the mITT population and repeated with per-protocol population as sensitivity analyses.

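### SAP 5.2.1 credits exposure to day 105 after a missed 3-month visit without requiring that status be known to that day, which biases the primary rate slightly low for participants with no later information (minor)

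*SAP*

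**What the plan says.** SAP 5.2.1 (under Non-infectious complications) ends each participant's exposure at the earliest of three dates.

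- **Removal:** the date of catheter removal for a listed reason.
- **Discontinuation:** "If a subject discontinues early, then the discontinuation date will be used to calculate the length of investigation duration".
- **3-month visit:** the visit date, capped at day 105. If "the subject misses the 3 months visit, then day 105 will be the end date of investigational period".

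The numerator is the number of observed complications, taken from the AE page by start date.

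Two protocol passages govern when a silent participant becomes discontinued. Section 8.1.1 says that a participant who stays unreachable is dated as follows: "he/she will be considered LTFU effective the date of the final failed contact attempt". It excludes from loss the case "where the participant misses one (1) follow-up visit but completes a subsequent one". Appendix A allows loss to be declared after three documented telephone attempts and, if necessary, a letter. In parentheses it adds that a participant may be considered lost "when participant misses two consecutive follow-ups and is unable to be contacted with the documented attempts outlined before".

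Other passages widen event capture. The Synopsis describes follow-up "via in-person or telephone visit to the participant and dialysis center", and sections 6 and 7 say much the same ("via in-person or telephone screen to the participant and dialysis center"). On possible loss, Appendix A adds: "The site should also contact the HD center to ascertain the" participant's status. Section 7.4.2 provides an eCRF for unscheduled access visits and asks for records when someone else treats a complication. Section 9.4 requires device-related AEs to be reported within one working day.

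**The concern.** A person-time rate is unbiased only if every day in the denominator is a day on which an event could have been recorded. The day-105 rule does not require this. It also gives a missed visit more exposure than an attended one: about 90 days for a visit on schedule, 105 for no visit.

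For a participant about whom nothing is learned after, say, the 1-month contact, the extra days are event-free by construction. The error runs one way, towards a lower complication rate. The per-protocol sensitivity analysis would not reveal it, because SAP 5.2.1 gives no other exposure rule for that population. Protocol 10.4.1 discusses missing data but sets no exposure rule. At stake are the primary estimate and interval, which protocol section 3 intends for labeling, and the test against 36.5 if the true rate is close to that goal.

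**Working it through.** **1. Does the discontinuation rule already cure it?** Take a participant last reached at day 30 who misses the 3-month visit, whose window closes at day 90 + 15 = 105.

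- If loss is declared only after the 6-month contact is also missed, it is dated after day 105. The credit is 105 days, of which 105 − 30 = 75 are unobserved.
- If the site declares loss sooner, with the last failed call on day 95 (assumed), the credit is 95 days, of which 65 are unobserved.

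Either way exposure ends at a failed contact, not at last known status.

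**2. When is day 105 right?** It is right when a later visit, a dialysis-center record or another source covers the gap, because protocol 7.4.1 records AEs since the last follow-up. Only participants with no later information from any source are affected. They include late enrollees with none yet when the 3-month analysis is run (SAP 5.2.2).

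**3. The plan's own figure.** Inputs from SAP 2.4: goal 36.5 and expected rate 31.5 per 1000 days, one-sided 0.025, type 2 error 0.2, attrition 15%. An exact Poisson test at 10,850 days has critical count 357, type I error 0.0250 and power 0.803. Then 10,850 / 0.85 = 12,765 days, and 12,765 / 90 = 141.8, so 142. The design figures reproduce. The issue is the exposure rule.

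**4. Size of the bias.** The documents give no number or timing of silent losses, so both are assumed. With m of 142 silently lost at day 30, the others observed for 90 days and a constant complication rate:

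- true days = (142 − m) × 90 + m × 30
- credited days = (142 − m) × 90 + m × 105
- inflation = credited / true − 1
- reported rate = true rate × true / credited
- critical count c = largest count with P(X ≤ c) < 0.025 at 0.0365 × credited days
- pass probability = P(X ≤ c) with mean true rate × true days

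| | m = 1 | m = 3 |
|---|---|---|
| True days | 12,720 | 12,600 |
| Credited days | 12,795 | 12,825 |
| Inflation | 0.6% | 1.8% |
| Critical count c | 424 | 425 |
| Reported rate at a true 36.5 | 36.3 | 35.9 |
| Type I error at 36.5 (with true days) | 0.031 (0.025) | 0.053 (0.023) |
| Reported rate at a true 31.5 | 31.3 | 30.9 |
| Pass probability at 31.5 (with true days) | 0.882 (0.862) | 0.923 (0.849) |
| Pass probability at 28 (with true days) | 0.9998 (0.9997) | 0.9999 (0.9996) |

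One loss at day 60 instead of day 30 gives 12,795 / 12,750 − 1 = 0.35% and a type I error of 0.028. A one-sided Wald test on the log rate, one reading of SAP 5.2.2, also gives 0.053 for m = 3.

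**The case against.** The strongest reply is that hardly anyone will be affected. Participants dialyse three times a week, so most have a center that knows their status. Counted events are AE-page entries by date and do not depend on attending the 3-month visit. To be affected, a participant must be unreachable, untraceable at the dialysis center, without any unscheduled-visit, outside or expedited report, and not discontinued early. Withdrawals and deaths already end exposure through the discontinuation rule. This stands, and it is why the point is minor.

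The boundary error rates also need an unlikely setting. A true 36.5 means 36.5 × 90 / 1000 = 3.3 complications per participant in 90 days. The feasibility data in protocol 2.1 suggest far less. Six device-related infections plus about 4 patency losses (9.1% of 44) over 44 × 180 = 7,920 days is about 1.3 per 1000. That is crude: one site, a different endpoint, and no allowance for deaths. At such a rate the test cannot change. This stands too.

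Three stronger readings might be inferred, and the documents do not support them.

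- **Two consecutive missed visits are needed before loss is declared.** Appendix A says this only in parentheses and with *may*; earlier declaration is allowed.
- **The planned 15% attrition is all silent loss.** It is a general attrition allowance, and much of it would be dated discontinuation. Type I errors computed from 10% to 15% silent loss should carry no weight.
- **Removal for infection or dysfunction also adds exposure, because SAP 5.2.1 does not list those reasons.** Protocol 7.5 keeps participants in the study only until the catheter is removed, which largely answers this. It is at most an ambiguity in wording.

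Finally, SAP Appendix 2 (derived data) is listed but was not available, and it may already limit the credit.

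**Conclusion.** The rule as written is a small flaw with a known direction. For participants with no information after a missed 3-month visit, unobserved days enter the denominator and the primary rate and interval are biased low. The number affected is not given and is probably small.

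Under the assumed 1 to 3 silent losses at day 30, exposure is inflated by 0.6% to 1.8%. The non-inferiority result is at risk only if the true rate lies roughly between 31.5 and 36.5 or just above. At 28 or below, the pass probability exceeds 0.999 with or without the extra days, and only the estimate moves slightly. It would be wrong to conclude that every missed visit biases the rate, or that the test's error rate is generally inflated. Severity: minor.

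**What to change.** In SAP 5.2.1, when the 3-month visit is missed, end exposure at the earlier of day 105 and the last date on which catheter and AE status is known. Credit day 105 only if a later contact or a dialysis-center record covers it. Keep the present day-105 rule as a sensitivity analysis and report how many participants it affects. If Appendix 2 already contains this limit, refer to it in 5.2.1.

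The cost is a clause of SAP text and some programming on contact, dialysis-session and AE dates that the study already collects. Exposure will be slightly shorter. There may be a small upward bias when a complication is itself the last contact; comparing the two analyses shows how much the choice of rule matters. If nobody is affected, the result is unchanged.

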### 5.2.2 Hypothesis Testing

The primary endpoint is the overall rate of infectious complications and noninfectious complications requiring revision to maintain patency and improve access performance at 3 months. Based on the DOPPS study data, competitor control devices had an average incidence rate of 31.5 complications per 1000 patient days. To show noninferiority of the Pristine™ Catheter, a 5 complications per 1000 patient days non-inferiority margin is used to establish a performance goal (PG) of 36.5 events per 1000 patient days.

The Primary Patency endpoint will be evaluated by the following hypothesis:

$H_0$ : The complication rate through 3 month is greater than or equal to 36.5 events per 1000 patients days at 3 months.

$H_1$ : The complication rate through 3 month is less than 36.5 events per 1000 patient days at 3 months.

That is:

$H_0: \lambda \geq \lambda_0$

$H_1: \lambda < \lambda_0$

Where  $\lambda_0$  is the PG of 36.5 events per 1000 patient days.

A one-sided p-value will be derived based on a Poisson distribution. The Pristine™ Catheter will be considered to have achieved the primary endpoint objective if the one-sided p-value is less than 0.025.

Conditioned on the success of the above test, a superiority test will be conducted to show that the Pristine™ Catheter is superior to the performance goal. The above test will be repeated with a PG of 26.5 events per 1000 patient days.

The analyses of the primary endpoint will be based on the mITT population and repeated with per-protocol population as sensitivity analyses. The analyses will be conducted after the last active treated subject completes their 3-month follow-up. The number of complications per 1000 patient days will be estimated by Poisson regression model with only the intercept term, and the estimate and 95% CI will be provided using the Wald method, and the p-value comparing to the PG will be calculated by a Chi-square test.

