10.5 Primary Endpoint

The combined primary endpoint is the overall rate of infectious complications and non-infectious complications requiring revision to maintain patency and improve access performance at 3 months. Based on the DOPPS study data, competitor control devices had an average incidence rate of 31.5 complications per 1000 patient days. To show non-inferiority of the Pristine™ Catheter, a 5 complications per 1000 patient days non-inferiority margin is used to establish a performance goal (PG) of 36.5 events per 1000 patient days.

The analysis of the primary endpoint will be based on the following test of Poisson rate:

H₀: The complication rate through 3 month is greater than or equal to 36.5 events per 1000 patients days at 3 months.

H₁: The complication rate through 3 month is less than 36.5 events per 1000 patient days at 3 months.

That is:

$$\mathbf{H_0: \lambda \geq \lambda_0}$$

$$\mathbf{H_1: \lambda < \lambda_0}$$

Where λ_0 is the PG of 36.5 events per 1000 patient days.

A one-sided p-value will be derived based on an Poisson distribution. The Pristine™ Catheter will be considered to have achieved the primary endpoint objective if the one-sided p-value is less than 0.025.

Conditioned on the success of the above test, a superiority test will be conducted to show that the Pristine™ Catheter is superior to the performance goal. The above test will be repeated with a PG of 31.5 events per 1000 patient days.

The analyses of the primary endpoint will be based on the ITT population and repeated with per-protocol population as sensitivity analyses.

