### Based on hypothesis test of Superiority

- Assumptions:
  - The complication rate of our performance goal is estimated at 31.5 events per 1000 patient days with a 90 days follow-up based on literature review, which is set as the performance goal.
  - The complication rate for the Pristine™ Catheter is assumed to be 26.5 events per 1000 patient days.
  - The attrition through 90 days is assumed to be 15%.

- The Type 1 error is 0.025 (one-sided).
- Sample Size:
  - Total exposure of 12765 patient days (which translates to 142 participants with average exposure of 90 days) will provide 85% power of the test (PASS 2019).

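### SAP 5.2.2 tests superiority against 26.5 per 1000 patient days, the rate assumed for Pristine, instead of 31.5, so the stated 85% power falls to about 2.4%

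*SAP*

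**What the plan says.** The primary analysis has two steps. The complication rate is first tested against 36.5 per 1000 patient days for non-inferiority. If that succeeds, the test is repeated against a lower goal for superiority. The documents disagree on the lower goal.

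- Protocol 10.5 (and the Synopsis, 1.1): "The above test will be repeated with a PG of 31.5 events per 1000 patient days".
- SAP 5.2.2: "The above test will be repeated with a PG of 26.5 events per 1000 patient days".
- SAP 2.4, superiority assumptions, on the goal: "The complication rate of our performance goal is estimated at 31.5 events per 1000 patient days with a 90 days follow-up". The same bullet goes on to say that this value is the performance goal.
- SAP 2.4, on the device: "The complication rate for the Pristine™ Catheter is assumed to be 26.5 events per 1000 patient days".
- SAP 2.4, on the result: the planned exposure "will provide 85% power of the test (PASS 2019)".

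Protocol 10.2 carries the same superiority assumptions as SAP 2.4. SAP 2.8 gives an acceptance criterion for non-inferiority only. The SAP revision history lists only version 1.0 and gives no reason for a different goal.

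**The concern.** In the superiority design, 31.5 is the null value (the benchmark attributed to DOPPS and the literature) and 26.5 is the alternative. SAP 5.2.2 uses the alternative as the null. The test then asks whether Pristine does better than the rate at which the plan powered it, and not whether it does better than the comparator benchmark. No part of either document derives 26.5 as a benchmark, and SAP 5.2.2 itself gives 31.5 as the competitor rate a few lines earlier.

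Superiority is a formal, gated and powered step, and the study results are intended for the device's labeling. If SAP 5.2.2 is followed, a catheter that performs at the rate assumed for this step would almost always fail it. If the protocol is followed, it would usually pass. Left unresolved, the question of which number governs would be settled after the event count is known.

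**Working it through.** **Inputs**

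- Superiority goal: 31.5 per 1000 patient days (Protocol 1.1, 10.5; SAP 2.4) or 26.5 (SAP 5.2.2).
- Assumed true Pristine rate for this test: 26.5 (SAP 2.4).
- Alpha: 0.025, one-sided (SAP 2.4).
- Exposure: 12,765 patient days, 142 participants at about 90 days (SAP 2.4).
- Attrition: 15% through 90 days (SAP 2.4). Taken off the exposure, T = 12,765 × 0.85 = 10,850 days.

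**Method.** This is a one-sample Poisson test. With goal λ0, success means X ≤ c events, where c is the largest count with P(X ≤ c | λ0·T) ≤ 0.025. Power at true rate λ1 is P(X ≤ c | λ1·T). The normal approximation is Φ{[(λ0 − λ1)√T − 1.96√λ0] / √λ1}.

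**1. Reproduce the plan's 85% (goal 31.5, true rate 26.5, T = 10,850).**
The expected count is 341.8 under the goal and 287.5 under the assumed rate. The critical count is 305, or 28.1 per 1000, and exact power is 85.5%.
Normal check: (0.005 × 104.16 − 1.96 × 0.1775) / 0.1628 = 1.06, and Φ(1.06) ≈ 85.6%.
The stated 85% reproduces. Taking attrition off the exposure is supported by the non-inferiority design: goal 36.5 and true rate 31.5 at 10,850 days give 80.3%, against the 80% implied by the stated type 2 error of 0.2.

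**2. Substitute the goal in SAP 5.2.2 (26.5, true rate 26.5).**
The critical count is 254, or 23.4 per 1000, and exact power is 2.4%. In the normal formula λ0 − λ1 = 0, so power is Φ(−1.96) = 2.5% at any exposure. The true rate lies on the null boundary, so power equals test size.

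**3. Without the attrition reduction (T = 12,765).**

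| Goal | Critical count | Boundary per 1000 | Power at true rate 26.5 |
|---|---|---|---|
| 31.5, T = 10,850 | 305 | 28.1 | 85.5% |
| 26.5, T = 10,850 | 254 | 23.4 | 2.4% |
| 31.5, T = 12,765 | 362 | 28.4 | 90.5% |
| 26.5, T = 12,765 | 302 | 23.7 | 2.4% |

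**4. How often the two documents would disagree.** At 10,850 days, 255 to 305 events is a success under the protocol and a failure under SAP 5.2.2. At a true rate of 26.5 the probability of landing there is 85.5% − 2.4% = 83.1%.

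**5. Rate needed to recover the power.** For 85% power against 26.5 the true rate would have to be about 22.0 per 1000 at 10,850 days, or about 22.3 at 12,765 days.

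**6. Does the test statistic matter?** SAP 5.2.2 also refers to an intercept-only Poisson regression with a Wald interval and a chi-square p-value. A one-sided log-scale Wald test at 10,850 days gives the same critical counts: ln(254/287.5) × √254 ≈ −1.98 and ln(305/341.8) × √305 ≈ −1.99, while one more event in either case falls short of −1.96.

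**The case against.** The contradiction in the text cannot be answered, but its consequences can be argued down.

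- **The error is conservative.** Any result that rejects 26.5 also rejects 31.5, so no false superiority claim against the benchmark can follow. This stands.
- **The scope for abuse is small.** The easier threshold is the one the protocol prespecified, at its own alpha, so reverting to it after seeing data would not inflate type I error against 31.5. This also stands. What remains is a question of credibility.
- **The primary objective is unaffected.** Success on the primary endpoint is defined by the 36.5 test, and the sample size comes from that test. Superiority is a conditional second step. This is true, but the step is still formal and carries a stated power.
- **The plan holds two assumed rates.** For non-inferiority, Pristine is expected to be near 31.5. At that rate superiority has only about 2.3% power even against 31.5. So the 2.4% figure applies under the superiority assumption, not under every assumption in the plan.
- **A much better device would pass either way.** Against 26.5 at 10,850 days, exact power is about 63% at a true rate of 23 and 99% at 20. The feasibility study hints at far lower rates. As a rough illustration, 6 device-related infections, 2 device-related general or access-site events and about 4 patency losses (9.1% of 44) make 12 events. Over an assumed 3,960 to 7,920 catheter days (44 × 90 to 44 × 180), that is about 1.5 to 3 per 1000. Definitions and population differ, so this is only indicative, but at such rates the discrepancy would not alter the result.
- **Neither document says which prevails.** The power is lost only if the SAP's number is the one used.

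These points limit the practical damage. None of them explains or reconciles the two thresholds.

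**Conclusion.** The concern holds. SAP 5.2.2 contradicts Protocol 1.1 and 10.5, and the SAP contradicts itself in section 2.4. If SAP 5.2.2 is followed, power at the assumed superiority rate of 26.5 drops from 85.5% to 2.4% at 10,850 days (from 90.5% to 2.4% at 12,765 days), and the boundary tightens by 51 events, from 305 to 254. The size of the loss rests on a true rate of 26.5, a one-sided alpha of 0.025 and Poisson counts. It does not depend on how attrition is handled. The direction is conservative and non-inferiority is untouched. It still has to be corrected before analysis, because it is the decision threshold of a confirmatory test and the documents give opposite answers over the range that contains the planned rate.

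**What to change.** In SAP 5.2.2, change the superiority goal from 26.5 to 31.5 events per 1000 patient days, to match Protocol 1.1, Protocol 10.5 and SAP 2.4. Record it in the SAP revision history with a date and reason, before the 3-month primary analysis is run. Stating the superiority threshold in SAP 2.8 as well would be useful but is optional.

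If 26.5 was in fact intended, the sponsor needs to justify it as a benchmark, amend the protocol and SAP 2.4 to agree, and restate the power.

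The correction costs one number in the SAP. Data collection, sample size and study conduct do not change.
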